6.11 Serious Adverse Drug Reactions

All SADRs are collected and reported to Shire Pharmacovigilance.

***Retrospective and prospective observational study of MRI changes in bone and visceral lesions of patients with type 1
Gaucher disease treated with VPRI[®] (velaglucerase alfa)***

The reference for safety information for this study is available in the French VPRI[®] SmPC.

A ***Serious Adverse Drug Reaction (SADR)***) is any untoward medical occurrence considered to be related to VPRI[®] at any dose:

- Results in death
- Is life-threatening

NOTE: The term ‘life-threatening’ in the definition of ‘serious’ refers to an event in which the subject was at risk of death at the time of the event; it does not refer to an event which hypothetically might have caused death if it was more severe.

- Requires inpatient hospitalisation or prolongation of existing hospitalisation
- Results in persistent or significant disability/incapacity
- Is a congenital abnormality/birth defect
- Is an Important Medical Event; Note: Important Medical Events that may not result in death, be life-threatening, or require hospitalisation may be considered an SADR when, based upon appropriate medical judgment, they may jeopardise the patient or may require medical or surgical intervention to prevent one of the other outcomes listed in this definition. In addition, suspected transmission (via marketed medicinal product) of any infectious agent is reportable to the Sponsor.

Examples of important medical events include allergic bronchospasm requiring intensive treatment in an emergency room or at home; blood dyscrasias or convulsions that do not result in inpatient hospitalisation; or development of drug dependency or drug abuse.

Hospitalisations, which are the result of elective or previously scheduled surgery for pre-existing conditions, which have not worsened after initiation of treatment, should not be classed as SADRs. For example, an admission for a previously scheduled ventral hernia repair would not be classed as SADRs; however, complication(s) resulting from a hospitalisation for an elective or previously scheduled surgery that meets the serious criteria must be reported if it qualifies as an SADR.

All SADRs are to be collected from the time the patient signs informed consent until the end of the 6-month study duration and it must be reported to the Sponsor/designee within 1 business day of the first awareness of the event.

The onset date of the SADR is defined as the date the event met serious criteria and the resolution date is defined as the date the event no longer met serious criteria, when the symptoms resolve, or the event is considered chronic or closed (i.e., when no further information is expected). In the case of hospitalisations, the hospital admission and discharge dates would be considered the onset and resolution dates, respectively.

Additionally, any signs or symptoms experienced by the patient prior to admission into the hospital or leading up to the onset date of the SADR and following the resolution date of the SADR, must be recorded as an ADR as appropriate, to identify individual seriousness and intensities.

Any SAE that results in the patient’s death (i.e., the SAE was noted as the primary cause of death) must have fatal checked as an outcome and the resolution date for that event is the date of death. For all other

***Retrospective and prospective observational study of MRI changes in bone and visceral lesions of patients with type 1
Gaucher disease treated with VPRI[®] (velaglucerase alfa)***

events ongoing at time of death that did not contribute to the patient's death, the outcome should be considered not resolved, without a resolution date recorded.

The physician/investigator is responsible to:

- Report all SADRs to Shire Pharmacovigilance department within one business day of the first awareness of the event.
- Complete, sign and date the Shire Clinical Trial Serious Adverse Event Form, verify the accuracy of the information recorded on the Shire Clinical Trial SAE Form with the corresponding source documents, and send a copy by fax to: ([name] or [name]) or email ([contact]) to the Shire Pharmacovigilance department.
- Notify, according to the local laws and requirements, any ethics committees (as applicable) and/or regulatory agencies, of:
 - SADRs that occur at his or her site, as required
 - All unexpected SADRs (15 Day Safety Reports) that occur during clinical trials with VPRI[®].

The physician/investigator is encouraged to discuss with Shire's Medical Monitor any ADRs for which the issue of relationship is unclear or questioned. Multiple inquiries between the Sponsor and/or the CRO and the study site may be necessary for report preparation.

The **Sponsor** must:

- Notify the relevant regulatory authorities/EU central Independent Ethics Committees (IEC) of unexpected SADRs
- Notify investigators of new relevant safety information that becomes available during any studies with VPRI[®]

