The study developed in conjunction with the French Referral Centers of Lysosomal Diseases and French Gaucher Treatment and Evaluation Committee (CETG: Comité d'Evaluation du Traitement de la Maladie de Gaucher) is a retro-prospective observational study of the French cohort of patients with type 1 Gaucher disease treated with VPTRIV® in everyday clinical practice.

It consists of two phases: a retrospective and a prospective one with an inclusion period of 1 year.

Phase I: retrospective phase

The retrospective period includes the period between the date of the baseline MRI to the patient's date of inclusion in the study. The reference MRI is defined as the closest MRI to the initiation of VPTRIV®, within the past five years, or within three months after initiation of VPTRIV®.

Phase II: prospective phase

Prospective period will be one year from the date of patient inclusion in the study.

The final MRI

MRI being performed in current practice every 2 years, the final MRI follow-up performed corresponds to those in the previous year or in the year following the patient's inclusion.

***Retrospective and prospective observational study of MRI changes in bone and visceral lesions of patients with type 1
Gaucher disease treated with VPRIV® (velaglucerase alfa)***

The duration of the study will be 2 years, 1-year inclusion period to be sure to include all patients VPRIV® (reviewed annually in consultation each year) and a prospective follow-up period of 1 year.

Provisional timetable for the study:

CCTIRS / CNIL authorisation	October 23, 2015
Inclusion of the first patient in the study	September 30, 2016
Inclusion of the last patient in the study	September 30, 2017
Last visit of the last patient	September 30, 2018
Study clinical report	January 31, 2019

Data collection and transmission

All data entered will be used for analysis purposes and results will be submitted to inform regulatory agencies. Patient care and management is freely determined by the participating physician, in the framework of an observational study reflecting the daily medical practice. The clinical data, the results of routine clinical and laboratory testing that are part of standard medical care for patients with Gaucher disease will be collected from the medical record of the patient :

- Socio-demographic characteristics
- History of the disease and context of diagnosis
- Medical background
- MRI: abdominal and bone, as defined below

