4.9 Overall Study Design and Plan

Figure 1. Overview of the Study Design

	0. Eligible patients (n= 40-50)	
	1. Patient inclusion (Written informed consent obtained)	
Retrospective data collection	
2. Retrospective data collection
 
The closest MRI conducted during the 5 years before the initiation of VPRIV® treatment or in the 3 months after the VPRIV® initiation is collected and corresponds to the reference MRI.
 
Clinical and biological data available 3 months before or after the reference MRI are collected
 
Medical history and clinical and biological data available, when VPRIV® treatment is initiated, are collected
 
Each MRI available since VPRIV® treatment initiation and patients inclusion is collected as well as clinical and biological data available 3 months before or after it
 
.....
 
MRI collected are anonymously sent to a central lab reading: MRI results data collection
	
Medical history
 
Clinical data
 
Laboratory data
 
VPRIV® treatment
 
MRI
 
..... VPRIV treatment
 
Centralized MRI reading:
 
 - Liver and spleen volumes - BMB score of the spine and femur
Prospective data collection	
3. Prospective follow-up:
 
For each MRI that will be conducted from the patient inclusion until the end of the one year follow up study, clinical and laboratory data available within the 3 months before the MRI and the 3 months after MRI are collected.
 
.....
 
.....
 
MRI collected are anonymously sent to a central lab reading: MRI results data collection
	
Clinical data
 
Laboratory data
 
VPRIV® treatment
 
MRI
 
.....
 
Centralized MRI reading:
 
 - Liver and spleen volumes - BMB score of the spine and femur
	
The study will last for one year from the date of the patient inclusion
 
The study is constituted of 2 phases: a retrospective and a prospective period
 
Phase I: Retrospective period
 
The retrospective period includes the period before VPRIV® treatment initiation until the beginning of this study..
 
Phase II: Prospective period
 
The prospective period will last for one year from the date of the patients inclusion
	

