4.12 Study Duration

The study is developed in conjunction with the French Referral Centers of Lysosomal Diseases, and the French Gaucher Treatment and Evaluation Committee (CETG: Comité d'Evaluation du Traitement de la maladie de Gaucher). It is a retro prospective observational study of the French cohort of patients with type 1 Gaucher disease treated with VPRIV® in everyday clinical practice.

It consists of two phases: a retrospective and a prospective phase with a 1 year inclusion period.

Phase I: retrospective phase

The retrospective period includes the period between the date of the baseline MRI to the patient's date of inclusion in the study. The reference MRI is defined as the closest MRI to the initiation of VPRIV®, within the past five years, or within three months after initiation of VPRIV®.

Phase II: prospective phase

Prospective period will be one year from the date of patient inclusion in the study.

The final MRI

MRI being performed in current practice every 2 years, the final MRI follow-up performed corresponds to those in the previous year or in the year following the patient's inclusion.

The duration of the study will be 2 years: a 1-year inclusion period to be sure to include all patients treated with VPRIV® (reviewed annually in consultation each year) and a prospective follow-up period of 1 year. Provisional timetable for the study:

CCTIRS / CNIL authorization	October 23, 2015
Inclusion of the first patient in the study	September 30, 2016
Inclusion of the last patient in the study	September 30, 2017
Last visit of the last patient	September 30, 2018
Study clinical report	January 31, 2019

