6.8 Safety Assessments

Safety of VPRIV® will be assessed according to ADRs, safety reporting associated with any medication given according to clinical routine. It should also be done according to local applicable drug law and using the procedures of the respective pharmaceutical manufacture.

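### Section 6.11 closes collection of serious adverse drug reactions after a 6-month study that the protocol does not define, and Section 8.7 dates the end of study 214 to 241 days before the planned last visit

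*Protocol*

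**What the plan says.** **Serious reactions.** Section 6.11 opens without a time limit: "All SADRs are collected and reported to Shire Pharmacovigilance". Later in the same section comes the operative rule: "All SADRs are to be collected from the time the patient signs informed consent until the end of the 6-month study duration". That sentence also carries the one-business-day deadline for reporting to the sponsor. The investigator's list of duties, further on in 6.11, repeats the deadline and gives no end date.

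**Other adverse drug reactions.** Section 6.10 restricts collection to the prospective part of the study and runs it from consent to the end of the study. It covers serious and non-serious reactions alike, and pregnancies have the same end point.

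**Length of follow-up.** The synopsis and Section 4.12 say: "Prospective period will be one year from the date of patient inclusion in the study". Section 4.9 agrees: "The prospective period will last for one year from the date of the patients inclusion". For the study as a whole, Section 4.12 says: "The duration of the study will be 2 years: a 1-year inclusion period", followed by one year of prospective follow-up.

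**Dates.** Under "Provisional timetable for the study", the synopsis and Section 4.12 list the same dates: first inclusion 30 September 2016, last inclusion 30 September 2017, "Last visit of the last patient" 30 September 2018, and study report 31 January 2019. Section 8.7 says that all the analyses are run when the study ends, and dates that end to February 2018.

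**The concern.** The six-month duration in Section 6.11 matches nothing in the design. The follow-up per patient is 12 months, the inclusion period is 12 months and the whole study is 24 months. The only other six-month span is the window of three months either side of an MRI for clinical and laboratory data (Section 6.6), which is not a study duration. Taken as written, serious reactions have a shorter collection window than non-serious ones. Sites then hold two end points for the same events, in the section they would consult for serious cases. Section 7.2 requires serious-event data in the clinical database to be reconciled with the pharmacovigilance database, and two windows invite mismatches there.

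In Section 8.7 the event (end of study) and the date (February 2018) cannot both hold. If the date were followed, the analysis would start before later-included patients had completed their year. MRIs still to come in that year, which Section 4.2 says are to be collected and which feed the primary endpoint, would be left out.

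**Working it through.** Only calendar arithmetic applies.

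**1. Is the timetable consistent with the stated design?**
- First to last inclusion: 30 Sep 2016 to 30 Sep 2017 = 365 days.
- Last inclusion to last visit: 30 Sep 2017 to 30 Sep 2018 = 365 days.
- Total: 365 + 365 = 730 days, the stated two years.

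The timetable therefore reproduces the design of one year of inclusion plus one year of follow-up. Neither the six months of 6.11 nor the February 2018 of 8.7 can be derived from it.

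**2. Days outside a six-month window for serious reactions.** For each patient this is (inclusion + 12 months) − (inclusion + 6 months), taking consent and inclusion as the same day.
- Inclusion on 30 Sep 2016: 30 Mar 2017 to 30 Sep 2017 = 184 days.
- Inclusion on 30 Sep 2017: 30 Mar 2018 to 30 Sep 2018 = 184 days.
- Over all 366 possible inclusion dates: 181 to 184 days out of 365, about half of the prospective year.

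**3. Where February 2018 falls.**

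| Interval | From 1 Feb 2018 | From 28 Feb 2018 |
|---|---|---|
| To the planned last visit (30 Sep 2018) | 241 days | 214 days |
| To the planned report (31 Jan 2019) | 364 days | 337 days |
| Since the planned last inclusion (30 Sep 2017) | 124 days | 151 days |

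The last-included patient would have 124 to 151 of 365 days of follow-up. Even on 28 February 2018, nobody included after 28 February 2017 would have completed the year. If accrual were uniform over the inclusion year (an assumption; the protocol does not say), the share of patients with a complete year would be 124/365 = 34% on 1 February and 151/365 = 41% on 28 February.

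**4. Does one error explain the other?** Six months after the last inclusion is 30 March 2018, which is 57 days after 1 February and 30 days after 28 February. It does not, so these are two separate errors.

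**The case against.** **Other text covers the gap.** Serious reactions are a subset of adverse drug reactions. Section 6.10 collects them all to the end of the study, and both the opening of 6.11 and its list of investigator duties are without limit. A site that follows the whole protocol has no licence to stop at month six, and the phrase may be just a wrong label for the study duration. This stands as far as consequence goes: the 181 to 184 days measure what lies outside the literal window, not days certain to be lost. It does not remove the contradiction. Section 6.8 helps little, since it refers to "safety reporting associated with any medication given according to clinical routine" and to local law and sets no window.

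**The February 2018 date is harmless.** Section 8.7 ties the analysis to the end of the study, and the timetable it conflicts with is labelled provisional. It is fair to rank this below the first point. But the timetable is the only one given, it appears twice in identical form, and it fits the design. The heading of 8.7, Interim Analysis, does not rescue the date, because the sentence places every analysis at study end.

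**Study duration is itself ambiguous.** It is one year per patient in Section 4.9 and two years overall in Section 4.12. That is true, but 6.10 confines collection to the prospective part, which is one year per patient. Neither meaning gives six months.

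**Impact on conclusions is limited.** The protocol has no safety objective, safety is to be described only, and 40 to 50 patients are expected. The primary bone marrow burden result does not depend on the serious-reaction window. This limits the severity and is accepted.

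**Conclusion.** Both contradictions hold in the current text; the protocol records no amendment, and neither is a product of redaction or text extraction. The six-month limit in Section 6.11 is the more important because it is an operative rule for collecting serious safety data. Taken literally, it leaves 181 to 184 of 365 prospective days outside the window for every patient, although Section 6.10 and the rest of 6.11 still cover that time. The date in Section 8.7 is 214 to 241 days too early against the planned last visit. It is a date correction of smaller consequence, but acting on it would mean analysing incomplete follow-up. The figures rest on the provisional timetable and on consent coinciding with inclusion. They should be fixed, but they do not threaten the study.

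**What to change.** - **Section 6.11:** delete the six-month qualifier and end the serious-reaction window at the end of the patient's prospective follow-up, so that it agrees with Section 6.10 and with the one-year prospective period. Using the same defined end point in 6.10 would also remove the ambiguity over study duration.
- **Section 8.7:** replace February 2018 with a statement that analysis follows the last visit of the last patient (planned for 30 September 2018) and database lock.

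The cost is two sentences in an amendment. No new data collection is needed, since Section 6.10 already has sites record adverse drug reactions through the prospective part.

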6.12 Removal of Patients from the Study

A patient's participation in the study may be discontinued at any time at the discretion of the Investigator. The following may be justifiable reasons for the Investigator to remove a patient from the study:

- Non-compliance, including failure to appear at one or more visits (or standard of care)
- The patient was erroneously included in the study
- The patient develops an exclusion criterion
- The patient suffers an intolerable adverse event
- The study is terminated by the Sponsor

The patient, the patient's parent(s), or the patient's legally authorized representative acting on behalf of the patient is free to withdraw consent and discontinue participation in the study at any time without prejudice to further treatment by the physician or at the institution. Discontinued patients should be followed according to medical practice standards.

If a patient or the patient's parent(s) or the patient's legally authorized representative(s) acting on behalf of the patient, discontinues participation in the study, or the patient is discontinued by the Investigator,

***Retrospective and prospective observational study of MRI changes in bone and visceral lesions of patients with type 1
Gaucher disease treated with VPRIV® (velaglucerase alfa)***

reasonable efforts will be made to follow the patient through the end of study assessments. The reason for refusal will be documented on the eCRF. Any adverse events (AE's) experienced up to the point of discontinuation must be documented on the AE eCRF. If AEs are present when the patient withdraws from the study, the patient will be re-evaluated within 30 days of withdrawal. All ongoing SAEs at the time of withdrawal will be followed until resolution.

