6.10 Adverse Events Assessments

Definition of Adverse Events/Adverse Drug Reactions, Period of Observation, Recording of Adverse Events/Adverse Drug Reactions

An **Adverse Event** (AE) is any untoward medical occurrence in a clinical investigation patient administered a product and that does not necessarily have a causal relationship with this treatment. An AE can therefore be any unfavorable and unintended sign (including an abnormal laboratory finding), symptom, disease or exacerbation of a pre-existing condition temporally associated with the use of a medicinal product.

Only AEs that will appear only in the prospective part of this observational study and which are considered to be related to Velaglucerase alpha are considered as ADRs, will be collected during this study, ADRs that will be related to the retrospective part of this study will not be collected. (See Section 7.1.2 for further guidance). An ADR is a response to a medicinal product which is noxious and unintended and which occurs at doses normally used in man for prophylaxis, diagnosis, and therapy of disease or for the restoration, correction, or modification of physiological function. Response in this context means that a causal relationship between a medicinal product and an AE is at least a reasonable possibility. Each ADR requires a complete and thorough description on the CRF.

All ADRs, including those associated with the protocol are collected from the time the informed consent is signed until the end of the study duration, are to be recorded on the

appropriate CRF and in source documents. Where possible, a diagnosis rather than a list of symptoms should be recorded. If a diagnosis has not been made then each symptom should be listed individually.

All ADRs (serious and non-serious) must be followed until closure (the patient's health has returned to his/her baseline status or all variables have returned to normal), an outcome is reached, stabilization (the Investigator does not expect any further improvement or worsening of the event), or the event is otherwise explained regardless of whether or not the patient is still participating in the study. When appropriate, medical tests and examinations are performed so that resolution of event(s) can be documented.

Severity Categorisation

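### Section 6.12 permits removal of a still-consenting patient for an intolerable adverse event or a missed visit, and its adverse-event scope does not match section 6.10 (minor)

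*Protocol*

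**What the plan says.** The synopsis of the protocol classes the study as non-interventional. Section 4.1 leaves care to the treating physician and takes the data from the medical record. Section 5.1 requires VPRIV treatment only at the start of the study.

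Section 6.12 says that participation "may be discontinued at any time at the discretion of the Investigator". It then gives reasons that may justify this. One is "Non-compliance, including failure to appear at one or more visits (or standard of care" (the protocol closes its bracket there); another is "The patient suffers an intolerable adverse event". Withdrawal of consent is treated in a separate paragraph, so the listed reasons reach patients who still consent. Whichever route is taken, "reasonable efforts will be made to follow the patient through the end of study assessments".

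On safety recording, 6.12 states: "Any adverse events (AE's) experienced up to the point of discontinuation must be documented on the AE eCRF". It adds a re-evaluation within 30 days for events present at withdrawal, and follow-up to resolution of serious adverse events (SAEs) ongoing at that time.

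Section 6.10 sets the scope for the whole study. It covers only events that arise in the prospective part and "which are considered to be related to Velaglucerase alpha are considered as ADRs, will be collected during this study". These adverse drug reactions (ADRs) "are collected from the time the informed consent is signed until the end of the study duration". They are followed until closure, an outcome or stabilisation is reached, "or the event is otherwise explained regardless of whether or not the patient is still participating in the study".

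**The concern.** Two things look wrong.

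First, the removal reasons suit a trial that administers a treatment and schedules visits, and this study does neither. An intolerable event may be a good reason to stop VPRIV, but it is no reason to stop reading the patient's record. The same holds for a missed visit. Section 4.10 justifies the design by the need to describe use, effect and safety in routine practice, and patients who tolerate the drug poorly are part of that description.

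Second, the two safety sections give sites different instructions. Read literally, 6.12 wants events of any cause for a patient who leaves, up to the day of leaving. Section 6.10 wants related events only, up to the end of the study. Section 8.5 plans a summary of adverse events under its primary safety heading, so entries collected to two different scopes could end up in one table.

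At stake are some months of prospective observation, possibly a final MRI, and a consistent safety listing.

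**Working it through.** The protocol states no removal rate or loss figure, so there is nothing to reproduce. The check is a comparison of the text, followed by a scale illustration.

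**Comparison of the text**

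1. *Does stopping VPRIV or missing a visit end eligibility?* No. Section 5.1 asks for treatment at the start, and 5.2 lists neither event.
2. *Does either prevent data collection?* No. The data come from the record (4.1), and MRIs are collected if routine care produces them (4.2).
3. *Is removal required?* No. Section 6.12 gives reasons that may justify it.
4. *Does collection end at removal?* Not by the text. The follow-up sentence in 6.12 expressly covers patients whom the investigator discontinues, but it does not say what is to be collected.
5. *Do the scopes agree?* No. Section 6.12 covers events of any cause, while the scope sentence of 6.10 covers related events only.
6. *Is the mismatch confined to 6.12?* No. Under severity and outcome, 6.10 itself speaks of recording AEs, for all patients.
7. *Do the time windows conflict?* Not plainly. The window in 6.10 runs to study end and makes no exception for removed patients. Section 6.12 states a duty up to discontinuation and does not forbid later entries. No sentence expressly addresses an ADR that starts after removal.

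**Scale of one removal**

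Inputs: 40 to 50 patients (8.2); a prospective period of 12 months; MRI every 2 years, with the final MRI in the year before or the year after inclusion (4.12).

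Assumptions: the final MRI is uniformly distributed over those 24 months; one patient is removed at month m; follow-up recovers nothing.

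Chance that the final MRI is still outstanding = (12 − m)/24. Dividing by the cohort size gives the share of all final MRIs.

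| Removal month | Chance outstanding | Share, 50 patients | Share, 40 patients |
|---|---|---|---|
| 1 | 11/24 = 45.8% | 0.458/50 = 0.92% | 0.458/40 = 1.15% |
| 6 | 6/24 = 25.0% | 0.25/50 = 0.50% | 0.25/40 = 0.625% |
| 11 | 1/24 = 4.2% | 0.042/50 = 0.08% | 0.042/40 = 0.10% |

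Prospective patient-months: 40 × 12 = 480 and 50 × 12 = 600. One removal at month 6 leaves 6 months, which is 6/600 = 1.00% to 6/480 = 1.25%. These are months of observation, not events.

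The figures illustrate one removal and are not upper limits. More removals, or earlier ones, raise them. Follow-up that succeeds lowers them, and so does a scan that routine care would never have produced, which is plausible for a patient who misses visits.

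**The case against.** The strongest reply is that the text already does most of what is asked. Removal is optional, follow-up is to be attempted for investigator removals as well, and 8.3 keeps every included patient in the analysis. The AE wording in 6.12 can be read as governed by the express scope sentence in 6.10, since the same loose usage appears within 6.10. All of this stands, and it is why the point is minor.

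Three stronger readings are tempting, and the documents do not support them.

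- *A reader might infer that data stop at removal and that the BMB result is biased.* The follow-up sentence contradicts the first part. For the second, the primary endpoint in 3.1 uses all follow-up MRIs, so an earlier follow-up scan can still contribute if the final one is lost. Nothing shows that removal is related to BMB change.
- *A reader might infer that removed and retained patients are ascertained under different rules.* That requires 6.12 to be read literally while the AE sentences of 6.10 are not. If all are read literally, retained patients too would have unrelated events recorded. The defect is inconsistent wording across both sections.
- *A reader might infer that an ADR starting after removal is lost.* The window in 6.10 contains no such exception. An explicit sentence would help, but the two sections are compatible.

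What the reply does not remove is that 6.12 names two reasons for removal that have no function in this design, and that its AE sentence does not match the stated scope.

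**Conclusion.** The point holds as a minor one. Section 6.12 permits, without requiring, the removal of a consenting patient for reasons that do not hinder record abstraction. Its AE sentence is wider than the scope in 6.10, and 6.10 is not consistent with itself.

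The case for a change rests on the text. The size is small: well under one final MRI for any single removal, under the uniform-timing assumption and with no recovery through follow-up. How many removals to expect cannot be derived from the protocol. Membership of the analysis set is unaffected, although 8.3 cannot supply data that were not collected.

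Serious reactions are better protected than non-serious ones, because 6.11 requires them to be reported on first awareness. That reassurance has a limit: the collection sentence in 6.11 refers to a 6-month study duration although the prospective period is one year. This is a separate matter, and a change to 6.12 would not resolve it.

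**What to change.** In section 6.12:

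- Delete the intolerable-adverse-event and non-compliance reasons.
- Do not treat a newly developed exclusion criterion as a reason to stop record abstraction. A new MRI contraindication ends further scans but not the rest of the record. Record the criterion and its date.
- State that patients who stop VPRIV or miss visits stay under routine-record observation, covering ADRs and any MRIs, to the end of their prospective year unless consent is withdrawn.
- Align the AE recording sentence to the scope and window of 6.10: related events, from consent to study end.
- Keep the 30-day re-evaluation and the follow-up of ongoing SAEs. They protect patients at exit, and consistency does not require removing them.

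In section 6.10, bring the severity and outcome wording into line with its own ADR scope sentence. Changing 6.12 alone would leave that inconsistency in place.

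The cost is an edit to the protocol wording and a few extra months of record abstraction for few patients. No visit, scan or analysis is added.
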